9.4.9 EXPLORATORY ANALYSES

Data collected after Month 36 will be considered exploratory analysis and summarized separately using descriptive statistics. Participants will be grouped by treatment pathway from the start of study through the re-randomization (original SYD-101 0.01% and SYD-101 0.03% participants) and transition to active treatment (original Vehicle participants) at Month 36:

- Participants initially randomized to SYD-101 0.01% at Baseline and re-randomized to SYD-101 0.01% at Month 36
- Participants initially randomized to SYD-101 0.01% at Baseline and re-randomized to Vehicle at Month 36
- Participants initially randomized to SYD-101 0.03% at Baseline and re-randomized to SYD-101 0.03% at Month 36

- Participants initially randomized to SYD-101 0.03% at Baseline and re-randomized to Vehicle at Month 36
- Participants initially randomized to Vehicle at Baseline and re-randomized to SYD-101 0.03% at Month 36

In general, data collected after Month 36 will be summarized according to the above groupings. As applicable, the groupings above may be further refined based on receipt of escape medication between Month 24 and Month 42 (inclusive). Changes in continuous measures will be relative to the data collection at the Month 36 visit, unless otherwise specified. Adverse events will be summarized separately for those events with onset after Month 36.

To evaluate the potential rebound effect once participants discontinue SYD-101 therapy, exploratory analyses will be conducted on the set of participants initially randomized to SYD-101 (0.01% or 0.03%) at Baseline who are re-randomized to Vehicle at Month 36. The mean annual progression rate from baseline to Month 36 will be numerically compared to the mean annual progression rate from Month 36 to Month 48 within this set of participants.

Select summaries will be provided for the group of participants initially randomized to SYD-101 (0.01% or 0.03%) at Day 1 (Baseline) and re-randomized to SYD-101 at Month 36 and who remain on SYD-101 for the entire duration of the study. This will be done to characterize the safety and efficacy profile of those participants receiving up to 48 months of SYD-101 treatment.

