All study-related raw data that support the corresponding tables and figures will be presented in data listings. Additional data listings may be generated as needed. All table, listing and figure shells will appear in landscape format employing Courier New 9-point font. Unless otherwise noted, all tables will summarize participant results by treatment group sorted in the following order: Vehicle, SYD-101 0.01% and SYD-101 0.03%. After receipt of escape therapy or re-randomization, participants will be summarized under current treatment with the treatment group divided to show initial and current treatment (e.g., Vehicle to Escape, SYD-101 0.01% re-randomized to Vehicle, etc.). Unless otherwise noted, all data listings will be sorted by treatment group and participant identification number defined as investigator identification number concatenated with the participant number. Due to family relocation or site closure, participants could be transferred from one site to a different site. In such cases, participant identification number will remain unchanged. Participants who changed study sites will be included in a data listing.

The baseline value for an assessment is defined as the last non-missing measurement including unscheduled assessments before or on the day of treatment with study drug (Day 1). Change from baseline is defined as the post-baseline value minus the baseline value for the given

assessment. Please also see Section 9 for details regarding baseline considerations for safety analyses when participants receive more than one treatment.

When study day is used for display or in comparisons, the following algorithm will be used:

- study day = date of assessment - date of first dose +1,
if date of assessment \geq first dose date.
- study day = date of assessment - date of first dose,
if date of assessment $<$ first dose date.

Note that the date of first dose is Day 1 and the day before the date of first dose is Day -1 (for analysis, there is no Day 0 for study day). First dose refers to first dose of any study treatment unless otherwise specified.

For all efficacy and safety analyses, analysis visit windows will be used for assigning assessments to an analysis visit, as per [Table 4-1](#) below.

Table 4-1 Visit Windows

Scheduled Visit	Target Day	Analysis Visit Window (Days)
Screening	-21 to 1	Not applicable
Day 1	1	Not applicable
Week 2	14	2 to 52
Month 3	91	53 to 136
Month 6	182	137 to 231
Month 9	280	232 to 322
Month 12	364	323 to 409

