For safety analyses from baseline to Month 24, the baseline will be considered the start of study prior to dose of any study medication. Unless otherwise specified, for safety analyses at Month 36, at Month 48, or from Month 36 to Month 48, data will be summarized based on treatment being taken at the time of event occurrence/assessment, including those who take SYD 101 0.03% as escape medication or who are re-randomized to Vehicle at Month 36. Participants who receive escape medication or who are re-randomized at Month 36 will be included under each treatment received during the analysis period. Percentages, if applicable, will be calculated based on the number of participants in the Safety Set who received at least one dose of the given treatment. For each treatment received, the baseline value will be the last non-missing assessment prior to initiation of the given treatment. (For participants originally randomized to SYD 101 0.03%, who are rerandomized to Vehicle at Month 36, and then subsequently switch to open label SYD 101 0.03% as escape medication, assessments made on SYD 101 0.03% will use the last non-missing value on or prior to Day 1/date of first SYD 101 0.03% treatment as baseline.) Total summaries will include data from assessments during the first 24 months while participants should be on their original randomized treatment only.

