9.1. Adverse Events

Treatment-emergent AEs are defined as those AEs or SAEs that occur after the start of study drug dosing. All TEAEs will be summarized by treatment group (SYD 101 0.01%, SYD 101 0.03%, or Vehicle) according to treatment taken at the time of event. Adverse events with onset set more than 30 days from date study treatment discontinuation will be summarized separately. In addition, all SAEs, including deaths, will be listed and summarized separately.

For the purpose of inclusion in TEAE tables, incomplete AE start and end dates will be imputed as follows:

Missing onset dates (where UK and UKN indicate unknown or missing day and month respectively):

- UK-MMM-YYYY: If the month and year are different from the month and year of the date of first dose, assume 01-MMM-YYYY. If the month and year are the same as the month and year for the date of first dose, and the end date (after any imputation) is on or after the date of first dose, then assume the date of first dose (Day 1). If the month and year are the same as the date of first dose, and the end date (after any imputation) is prior to the date of first dose, then assume the end date for the start date.
- DD-UKN-YYYY/UK-UKN-YYYY: If the year is different from the year of the date of first dose, assume 01-JAN-YYYY of the collected year. If the year is the same as the date of first dose year, and the end date (after any imputation) is on or after the date of first dose, then assume the date of first dose (Day 1). If the year is the same as the date of first dose, and the end date (after any imputation) is prior to the date of first dose, then assume the end date for the start date.

Missing end dates (where UK and UKN indicate unknown or missing day and month respectively):

- UK-MMM-YYYY: Assume the last day of the month;
- DD-UKN-YYYY/UK-UKN-YYYY: Assume 31-DEC-YYYY

All adverse events will be classified by System Organ Class and Preferred Term (PT) according to the Medical Dictionary for Regulatory Activities (MedDRA, Version 21.0 or higher).

An overview summary of the number and percentage of participants with any TEAE, serious TEAE, treatment-related TEAE, treatment-related serious TEAE, TEAE leading to drug withdrawal, TEAE leading to study discontinuation, and AE leading to death will be provided by treatment group. The overall summaries will be presented for all adverse events, all ocular events, and all non-ocular events.

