9.1.1. Incidence of Adverse Events

Summaries that are displayed by system organ class (SOC) and preferred terms will be ordered by descending incidence of SOC and preferred term within each SOC. Summaries displayed by preferred term only will be ordered by descending incidence of preferred term. Incidence summaries will be presented separately for ocular and non-ocular events. For ocular summaries,

a participant will be counted once for the given level of summary if the participant experiences the event in either eye. Summaries of the following types will be presented:

- Overall summary of number of unique TEAEs and treatment-emergent SAEs
- Overall summary of number of unique TEAEs and treatment-emergent SAEs by subgroup (Age, Sex, Race and Iris Color)
- Participant incidence of TEAEs by MedDRA SOC and preferred term
- Participant incidence of TEAEs by MedDRA SOC and preferred term
- Participant incidence of TEAEs by severity grade, MedDRA SOC, and preferred term
- Participant incidence of TEAEs by relationship to study drug, MedDRA SOC, and preferred term
- Participant incidence of severe TEAEs related to study drug by MedDRA SOC and preferred term
- Participant incidence of SAEs by MedDRA SOC and preferred term
- Participant incidence of non-serious AEs by MedDRA SOC and preferred term
- Participant incidence of AEs leading to discontinuation of study drug by MedDRA SOC and preferred term

At each level of summarization (e.g., any AE, SOC, and preferred term), participants experiencing more than one TEAE will be counted only once. In the summary of TEAEs by severity grade, participants will be counted once at the highest severity reported at each level of summarization; in the summary of TEAEs by relationship, participants will be counted once at the closest relationship to study drug. Related events include those reported as “Possibly Related” or “Related” to study drug; events considered not related are those reported as “Unlikely” or “Not Related” to study drug.

At the Month 36 and Month 48 analysis, adverse events will be assigned based on the treatment being taken at the time of the event. If an event occurs after a participant is on escape medication, the event will be assigned to the SYD-101 0.03% treatment group regardless of the randomized treatment.

Additionally, adverse events will be summarized separately for those events with onset after Month 36. Events will be assigned based on the treatment being taken at the time of the event.

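### The SAP does not say which display governs the cumulative Month 48 adverse event tables; under one permitted reading, equal risk would look higher on SYD-101 0.01% than on Vehicle

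*SAP*

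**What the plan says.** Three places bear on AE tables once participants have changed treatment.

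- **SAP 9, 9.1 and 9.1.1.** At Month 36 and Month 48, safety data follow the treatment in use when the event occurs. A switcher counts under each treatment received, and percentages are "calculated based on the number of participants in the Safety Set who received at least one dose of the given treatment". The columns are named: "All TEAEs will be summarized by treatment group (SYD 101 0.01%, SYD 101 0.03%, or Vehicle) according to treatment taken" at the time of the event. SAP 9.1.1 repeats the rule: "At the Month 36 and Month 48 analysis, adverse events will be assigned based on the treatment being taken at the time of the event". For events on escape medication, "the event will be assigned to the SYD-101 0.03% treatment group regardless of the randomized treatment". No AE rate per unit of time on treatment is planned.
- **SAP 4.** After escape or re-randomization, "participants will be summarized under current treatment with the treatment group divided to show initial and current treatment".
- **Protocol 9.4.9.** Five pathways are listed (initial treatment, then Month 36 assignment), and "In general, data collected after Month 36 will be summarized according to the above groupings". AEs are mentioned in the same paragraph. SAP 8.3 repeats the pathways under efficacy only.

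The SAP 9 rule is introduced as a default that yields to other specifications, and the table conventions in SAP 4 are also introduced as defaults. SAP 11 records no change to the AE grouping.

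Some planned displays limit the problem. Month 24 tables use the original assignment. On totals, "Total summaries will include data from assessments during the first 24 months while participants should be on their original randomized treatment only". SAP 9.1.1 adds that "adverse events will be summarized separately for those events with onset after Month 36". SAP 7.3.1 summarizes exposure to each treatment by initial arm and counts participants on each treatment at each visit.

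**The concern.** The protocol's first clinical hypothesis judges safety by AE incidence and severity against Vehicle. At Month 36 half of each active arm moves to Vehicle and the whole Vehicle arm moves to 0.03%; nobody moves into 0.01%. In a cumulative Month 48 table with three undivided columns, 0.01% therefore contains only participants planned for 36 or 48 months on that treatment. The other two columns mix long-term participants with 12-month switchers. A percentage with at least one AE rises with time at risk, so the columns are not comparable even when the drug does nothing. A programmer could follow SAP 9 to 9.1.1, SAP 4 or protocol 9.4.9 and produce materially different tables, each supported by some part of the documents.

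**Working it through.** **Inputs from the documents.** 280 per arm (SAP 4.1); 1:1:1 allocation and the Month 36 rules (SAP 3.1); 7% yearly dropout or treatment discontinuation, and annual progression rates of 0.65 D (Vehicle) and 0.325 D (active) with SD 0.55 D (SAP 4.1 simulation). The documents give no AE rate or AE exposure figure to reproduce. The 280 per arm agrees with its stated power: 0.18/(0.60 × √(2/280)) = 3.55; 3.55 − 2.24 = 1.31, which gives 90.5%.

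**Assumptions not in the documents.** The same first-event hazard in every arm, restarted at each new treatment; no escape use unless stated.

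**Step 1, exposure (0.01% / 0.03% / Vehicle).** Without dropout the denominators are 280 / 560 / 560.
- 0.01%: (140×4 + 140×3)/280 = 3.5 years
- 0.03%: (140×4 + 140×3 + 280×1)/560 = 2.25 years
- Vehicle: (280×3 + 280×1)/560 = 2.0 years

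If the 7% is all dropout, 0.93³ = 0.804 reach Month 36. The denominators become 280 / 505 / 505 and the means 3.08 / 2.14 / 1.92 years. No AE rate is needed for this step.

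**Step 2, percentages at equal risk.** Let R(t) be the probability of at least one event in t years on treatment.
- 0.01% = [R(4) + R(3)]/2
- 0.03% = [140R(4) + 140R(3) + 280R(1)]/560
- Vehicle = [R(3) + R(1)]/2

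Constant hazard: R(t) = 1 − exp(−ht), with h = 0.119 per year so that R(3) = 30%; then R(1) = 11.2% and R(4) = 37.8%. With dropout, c = −ln 0.93 = 0.0726 and F(t) = h/(h+c) × [1 − exp(−(h+c)t)] replaces R(t), with switchers weighted by 0.804. Early clustering: R(t) = 1 − exp(−Lt^k), with L set so that R(3) = 30%; k = 0.5 puts 58% of the 36-month cumulative hazard in year 1.

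| Scenario | 0.01% | 0.03% | Vehicle | 0.01%/Vehicle |
|---|---|---|---|---|
| Constant, no dropout | 33.9 | 22.6 | 20.6 | 1.65 |
| Constant, 7% dropout | 30.2 | 21.5 | 19.9 | 1.52 |
| k = 0.5, no dropout | 31.9 | 25.2 | 24.3 | 1.31 |
| k = 0.5, 7% dropout | 29.6 | 24.5 | 23.7 | 1.25 |
| k = 0.25, no dropout | 30.9 | 27.3 | 26.9 | 1.15 |
| k = 0.25, 7% dropout | 29.6 | 26.9 | 26.5 | 1.12 |

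Over constant hazards from 0.02 to 0.40, the ratio runs from 1.73 down to 1.46 without dropout and from 1.59 down to 1.37 with it. The 0.03% minus Vehicle difference never exceeds 2.5 points.

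**Step 3, neighbouring tables in the same model (h = 0.119, no dropout).** The Month 36 table gives 30/30/30% without escape. The post-Month 36 table gives 11.2% in every column if its denominator is those on each treatment in that period.

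**Step 4, escape at Month 36.** Take normally distributed progression rates at the SAP planning values. A start at Month 24 needs 1.5 × rate ≥ 2.00 D (10.7% of Vehicle, 3.3% of 0.01%). A start at Month 30 needs 2 × rate ≥ 2.00 D (a further 15.5% and 7.6%). With retention 0.93² and 0.93^2.5, full uptake gives about 88 switchers into 0.03%. At 30% risk with dropout, 0.03% minus Vehicle moves from 0 at no uptake to −3.3 points at full uptake.

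**Step 5, the Month 36 data cut.** SAP 4 admits events up to 28 days after the Month 36 visit. SAP 4.2 keeps the re-randomization masked until the Month 48 lock, so current treatment is unknown for such events in the active arms. Participants per arm with an AE in those days: 280 × 0.804 × [1 − exp(−0.119 × 28/365.25)] = 2.0. Requiring no earlier AE multiplies this by exp(−3 × 0.119) and gives 1.4. At hazard 0.40 the two counts are 6.8 and 2.0.

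**Step 6, two further rules.** SAP 9.1.6 divides each year's AEs by the whole Safety set. If the 7% is all loss to follow-up, Year 3 and Year 4 percentages are understated by 1 − 0.93^(774/365.25) = 14% and 1 − 0.93^(1138/365.25) = 20%. If half is loss, the figures are 7% and 11%; if none, zero. SAP 7.3.1 runs overall Month 24 and Month 36 exposure to the visit date. If instead the 7% all stop drug but stay in the study, exposure is overstated by 2/1.862 − 1 = 7.4% and 3/2.696 − 1 = 11.3%; at half, 3.6% and 5.4%; if none, zero. The two extremes cannot both hold.

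**The case against.** The best defence is that SAP 4 and SAP 9 fit together: both use current treatment, Section 9 fixes event assignment and denominators, and nothing in it cancels the Section 4 split. Read so, the pooled columns never appear. That reading is available, but the SAP does not state it, and SAP 9.1 and 9.1.1 name three groups. Protocol 9.4.9 is also qualified as general, covers only post-Month 36 data, and does not describe a cumulative Month 48 AE table. It is therefore a different display rather than a flat contradiction.

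A reader might infer that the pooling is settled, or that the safety comparison for either submission is distorted. The documents support neither. The EU submission rests on the Month 24 lock and the US submission on the Month 36 lock, both before the randomized-withdrawal data are analyzed. Post-Month 36 data are exploratory, and AE summaries are descriptive. A reader might also infer that 0.03% would be misrepresented against Vehicle, but both columns are diluted alike and the difference stays within 2.5 points.

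Three further objections stand. The size depends on a hazard that the documents do not give, and it shrinks when events cluster early. Person-year rates are no cure: at k = 0.5 they would show 0.01% at 0.78 of Vehicle with no drug effect. On the smaller items, the 28-day events fall inside the protocol's 30-day window for treatment-emergent AEs, so attribution to the initial arm is defensible. The annual denominator understates all arms alike if dropout is similar. Exposure to each treatment by last dose is already planned.

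**Conclusion.** The concern holds as an unresolved choice of display for the cumulative Month 48 AE tables. The exposure imbalance (3.5/2.25/2.0 years, or 3.08/2.14/1.92 with 7% yearly dropout) follows from the design if the three columns are applied without the Section 4 split. The apparent excess on 0.01% is conditional on that reading and on an assumed hazard: a ratio of about 1.4 to 1.7 if constant, about 1.1 to 1.3 if events come early. Month 24 tables and the separate post-Month 36 table are not materially affected, and Month 36 tables are affected only by escape use, whose uptake is unknown. The masked 28-day events are few, about 1 to 2 participants per arm at the assumed hazard, but the rule cannot be carried out for them in the active arms. The annual-denominator and overall-exposure rules are minor, and their size depends on how the 7% splits between leaving the study and stopping drug. This is worth correcting before the Month 48 tables are built; it does not touch efficacy or sample size.

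**What to change.** 1. State in SAP 9 that Month 36 and Month 48 AE tables are split by initial and current treatment as in SAP 4, and align this with the pathways in protocol 9.4.9.
2. Add one AE table by randomized arm, censored at the first treatment switch (escape or re-randomization). Its downside is some lost Vehicle follow-up where escape is used, about 1.3 points at full uptake and 30% risk. Person-year rates are optional and supplementary only.
3. At the Month 36 analysis, show AEs with onset after re-randomization separately by initial arm, without dropping them.
4. In SAP 9.1.6, use participants followed into each annual period as the denominator.
5. In SAP 7.3.1, end overall Month 24 and Month 36 exposure at the earlier of last dose and cut-off.

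The cost is SAP wording and a few tables or columns. Dosing dates and exposure to each treatment are already derived, and trial conduct does not change.

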2.3 RISK/BENEFIT ASSESSMENT

2.3.1 KNOWN POTENTIAL RISKS

There have been many long-term studies using atropine 1% chronically in children as young as 3 years old with no significant adverse events (AEs) ([Paediatric Eye Disease Investigator Group 2002](#), [Chua 2006](#), [Li 2009](#), [Scheiman 2008](#), [Tong 2009](#)). Common side effects with atropine 1% include photophobia and blurred vision due to cycloplegia ([SmPC, Minims Atropine Sulfate 1% Eye Drops, solution, Pan 2012](#)), dry eye, burning/stinging, tearing, and increased heart rate and blood pressure. More dilute concentrations have been well tolerated ([Shih 1999](#)) with allergic conjunctivitis reported only in the 0.5% and 0.1% treatment groups ([Chia 2012](#)). Upon cessation of atropine 1% after 2 years of treatment in the ATOM1 study, there was a marked rebound on the myopia progression ([Tong 2009](#)), but even at 3 years of follow-up, the treated group had significantly less myopia than the control group.

More dilute concentrations have been well tolerated ([Shih 1999](#)) with allergic conjunctivitis reported only in the 0.5% and 0.1% treatment groups ([Chia 2012](#)). In the ATOM2 study, the low-dose atropine (0.01%) had a minimal loss of accommodation (2-3 D), minimal pupil dilation (0.8 mm), and no effect on near visual acuity ([Chia 2012](#)). Clark ([2015](#)) reported 2 cases of intermittent light sensitivity to bright sunlight and 1 case with a history of migraine headaches with intermittent blurred vision; no case was symptomatic enough to warrant discontinuation of atropine 0.01%. In a study conducted in Spain ([Diaz-Llopis 2018](#)), 2% of the atropine 0.01%-treated patients discontinued medication due to AEs, including photophobia, reading difficulty, mydriasis, and headaches; up to 5% of patients reported slight photophobia, difficulties in very near reading, and excessive mydriasis that did not require treatment withdrawal. Gong and colleagues conducted a meta-analysis of 19 peer-reviewed studies on the efficacy and AEs of atropine in childhood myopia; no corneal AEs were identified with any strength and there were no differences in the incidence of AEs between Asians and Caucasians ([Gong 2017](#)).

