9.2. Vital Sign Measurements

Summary tables will be presented for vital sign data, including systolic blood pressure (mmHg), diastolic blood pressure (mmHg), temperature (C), heart rate (bpm), height(cm) and body weight(kg) by treatment group and overall for participants in the Safety set. Observed results at each visit and changes from baseline to each scheduled post-baseline visit will be presented. All vital sign data by participant will be presented in a listing.

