9.3.4. Pupil Diameter

Pupil Diameter will be measured prior to any cycloplegia using a hand-held pupil card provided to the sites and the result in 0.5 mm increments will be recorded on the eCRF. Descriptive statistics for pupil diameter and changes from baseline at each assessment time point will be presented by randomized treatment. For analysis, the average of the right and left eyes will be used.

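### At Month 48 the vital-sign change columns cover about 48 months for children who continue SYD-101 but about 12 months for children withdrawn to Vehicle, so growth and age trends distort that comparison

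*SAP*

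**What the plan says.** SAP Section 9 has two safety baselines. Through Month 24, baseline is the start of the study. The later analyses are grouped by current treatment ("for safety analyses at Month 36, at Month 48, or from Month 36 to Month 48, data will be summarized based on treatment"). The SAP then fixes the reference point for each such group: "For each treatment received, the baseline value will be the last non-missing assessment prior to initiation of the given treatment". A child who leaves 0.03% and later returns to it as escape goes back to the first baseline: "assessments made on SYD 101 0.03% will use the last non-missing value on or prior to Day 1/date of first SYD 101 0.03% treatment". For a child who never leaves the assigned dose, baseline is therefore the pre-Day 1 value.

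The general baseline definition in SAP Section 4 does not override this. It refers the reader to Section 9 for "details regarding baseline considerations for safety analyses when participants receive more than one treatment".

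For blood pressure, heart rate, height and weight, SAP 9.2 says only "Observed results at each visit and changes from baseline to each scheduled post-baseline visit will be presented". Where the authors wanted different handling, they wrote it. SAP 9.3.4, for example, reads "Descriptive statistics for pupil diameter and changes from baseline at each assessment time point will be presented by randomized treatment", which is an exception on grouping.

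The protocol differs. Section 9.4.4 gives vital signs a single baseline, the last value before the first dose of study drug. Section 9.4.9, on data after Month 36, says "Changes in continuous measures will be relative to the data collection at the Month 36 visit, unless otherwise specified". SAP 8.3 keeps that Month 36 reference, but only for efficacy. SAP Section 11 does not list the safety baseline among the changes from the protocol.

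**The concern.** At Month 36 the children on each SYD-101 dose are re-randomized 1:1 to stay on it or to receive Vehicle, and all original Vehicle children not on escape move to 0.03%. Continued versus withdrawn, within a dose, is therefore the only randomized contrast in the fourth year.

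The vital-sign change columns for its two sides cover different lengths of time. Children grow taller and heavier, and their heart rate and blood pressure may also move with age. A 48-month change set beside a 12-month change mixes about three extra years of ageing with any drug effect.

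Protocol 2.3.1 lists "tearing, and increased heart rate and blood pressure" among the common side effects of atropine 1%. At 0.01% and 0.03% this is a potential risk, which is a reason to measure it cleanly. Change from baseline in vital signs is a named safety endpoint in both documents.

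**Working it through.** The plan states no figure for this point, so there is none to reproduce. The check follows the baseline rule through the visit schedule.

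**Inputs from the documents**
- Target days in SAP Table 4-1: Day 1, Month 36 = day 1092, Month 48 = day 1456.
- Vital signs are taken at Screening and at Months 12, 24, 36 and 48 (schedules in both documents). The pre-treatment reading is a Screening value, up to 21 days before Day 1; this is ignored below.
- 280 children per arm (Protocol 9.2), re-randomized 1:1 within each SYD-101 dose (Protocol 4.1).

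**Assumptions, not in the documents**
- Age drift g of 1 to 3 units per year, taken as a fall for heart rate.
- As an alternative for blood pressure, a rise of 0.5 to 2 mmHg per year.
- A drug effect d that is present on drug and gone by Month 48 after withdrawal.

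**Step 1: interval behind the Month 48 change**

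| Pathway | Children (before dropout and escape) | Baseline | Interval |
|---|---|---|---|
| 0.01% continued | 140 | Day 1 | 1456 − 1 = 1,455 days (3.98 years) |
| 0.03% continued | 140 | Day 1 | 1,455 days (3.98 years) |
| 0.01% to Vehicle | 140 | Month 36 | 1456 − 1092 = 364 days (1.00 year) |
| 0.03% to Vehicle | 140 | Month 36 | 364 days (1.00 year) |
| Vehicle to 0.03% | 280 | Month 36 | 364 days (1.00 year) |

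The excess is 1,455 − 364 = 1,091 days, or 2.99 years. This step needs no assumption about drift or effect.

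**Step 2: what the difference in change estimates**
- SAP rule: the continued change is 3.98g + d (off drug to on drug). The withdrawn change is 1.00g − d (on drug to off drug). Difference = 2.99g + 2d.
- Common Month 36 reference: continued g, withdrawn g − d. Difference = d.
- Common Day 1 reference: continued 3.98g + d, withdrawn 3.98g. Difference = d.

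Either common reference removes the drift. The SAP rule keeps about three years of it and doubles d.

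**Step 3: numbers**
- d = 0, heart-rate drift −1 to −3 bpm per year: 2.99 × (−1) to 2.99 × (−3) = −3.0 to −9.0 bpm.
- d = 0, blood-pressure drift +0.5 to +2 mmHg per year: +1.5 to +6.0 mmHg.
- d = +2 bpm (illustrative), drift −1, −2, −3: −2.99 + 4 = +1.0; −5.97 + 4 = −2.0; −8.96 + 4 = −5.0 bpm. The true difference is +2 in each case.

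The same artefact applies within 0.01% and within 0.03%.

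**Step 4: reach**
Through Month 24 the baseline is the start of the study. At Month 36, a child not on escape has had one treatment, begun on Day 1, so the rule gives the same baseline. Only children whose treatment changed through escape differ: one who moves to 0.03% at Month 24 has a 12-month change at Month 36, against 36 months for those on 0.03% from Day 1.

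**The case against.** Much of the case for leaving the plan alone is sound.

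- The same table shows observed values at each visit. Re-randomization balances age in expectation, so Month 48 values in continued and withdrawn children can be compared without a baseline. This stands: only the change columns are distorted.
- Vital signs get descriptive statistics, and data after Month 36 are exploratory. This stands. A reader might express the artefact in standard errors and infer a false-positive finding, but the plan specifies no test or decision rule for it.
- A reader might infer that a known cardiovascular harm will be misreported. The documents do not support that. The protocol names the effect for atropine 1% and says more dilute concentrations were well tolerated.
- A reader might also average all children on 0.03% at Month 48, giving (140 × 48 + 280 × 12)/420 = 24 months. SAP Section 4 divides treatment groups by initial and current treatment, so that pooled column is not what is planned. The division prevents pooling, but it still leaves 48-month and 12-month columns side by side.
- Protocol 9.4.9 states its Month 36 reference as a general rule that allows exceptions, and SAP Section 9 could be one. That softens this conflict. The single vital-sign baseline in Protocol 9.4.4 carries no such allowance.

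**Conclusion.** The point holds for the Month 48 change-from-baseline columns for vital signs. The mismatch of about 1,455 against 364 days follows from the SAP's own rule and target days.

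Its effect on heart rate and blood pressure depends on assumed drift: about 3 to 9 units at 1 to 3 units per year, or 1.5 to 6 mmHg if blood pressure drifts by 0.5 to 2 mmHg per year. That could hide or reverse a modest rise in heart rate, or mimic a rise in blood pressure, for anyone reading those columns alone. For height and weight the direction of the distortion is plain, because the children are growing.

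The vehicle-controlled evidence through Month 36 is sound apart from escape users. This is a table-specification fault worth correcting before the Month 48 analysis. It does not threaten the trial's safety conclusions as a whole.

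**What to change.** In SAP 9 and 9.2, tabulate the Month 48 vital-sign change by the five pathways in Protocol 9.4.9, with the same reference for every pathway:

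- Month 36 to Month 48, for continued versus withdrawn children within each dose.
- Day 1 to Month 48, for cumulative change. This is needed because the Month 36 value is on-drug for continuing children, so a sustained effect would appear as no change within that group.

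Flag data collected after escape, including in the Month 36 table. Reconcile SAP Section 9 with Protocol 9.4.4 and 9.4.9, and record any remaining departure in SAP Section 11.

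Vital signs are already scheduled at Months 36 and 48, so no new data are needed. The cost is SAP wording and one extra set of table columns.
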